## **11.0 Number of Participants**

### **11.1 Number of Participants to be Consented:**

For formative assessment focus groups, a maximum number of 16 (minimum of 12) participants will be enrolled for an average of 6-8 participants for each of the two focus groups.

For the pilot RCT, a maximum number of 60 (minimum of 54) participants will be enrolled for an average of 27-30 participants for each of the intervention and control groups. Participants enrolled in the intervention condition will be consented to participate in the yoga intervention eligible and the post-intervention focus groups.

## **12.0 Recruitment Methods**

### **12.1 Recruitment Process:**

Participants will be recruited using radio and print newspaper advertisements in media outlets with a predominantly African-American audience; social media (e.g., Facebook, Instagram, and Twitter) posts targeting local, African-American individuals, groups and organizations; email blasts distributed to local churches, community centers, libraries, and community organizations (particularly health organizations such as NorthPoint Health & Wellness Center, Smiley's Clinic, Whittier Clinic) that serve African-Americans and/or women in the North Minneapolis area of Minnesota. All recruitment materials will have culturally appropriate representations of African-American women and examples are provided in this application.

### **12.2 Source of Participants:**

Participants will be drawn from the greater Twin Cities, MN area.

### **12.3 Identification of Potential Participants:**

All recruitment materials will have contact information (phone number and email address) that interested participants will use to express their desire to be involved in the study. All potential participants must self-identify as an African-American woman over the age of 18.

Initial contact with prospective participants will be made by study team members listed on the IRB application; these research staff members will be trained by the PIs to properly screen participants.

### **12.4 Recruitment Materials:**

Materials that will be used to recruit participants and are included in this application are:

- Flyer to be distributed via email and social media
- Text for social media posts
- Text for print newspaper posts
- Transcript for recorded radio posts

#### 12.5 Payment:

For the formative assessment focus groups, each participant will receive \$25 as a thank you for their feedback and time.

For each data collection timepoint, each participant will receive \$50 for completing assessments, which includes wearing activPAL for 7 days; collecting two salivary samples; having blood pressure, height, weight, and body fat % measured by trained staff; and completing an electronic survey. After completing the in-person baseline assessment, each participant will receive \$5 to complete an online survey. There are three data collection timepoints: baseline, post-intervention, and 3-month follow-up. Therefore, pilot RCT participants (both intervention and control participants) are able to receive up to \$255 for completing measurements.

Another incentive pilot RCT participants will receive yoga equipment that they will own. Participants assigned to the intervention group will receive a yoga mat, a yoga strap, a yoga bolster, a pair of yoga blocks, and a bag for carrying at the first in-person yoga session. Participants assigned to the control condition will receive their yoga equipment at the 3-month follow-up data collection as a thank you for participating in the study. Furthermore, since the control participants were not involved in the face-to-face yoga intervention, they will receive a three-month membership to a local yoga studio and a catalog of virtual yoga classes led by the intervention yoga instructors. The membership and catalog may assist the control participants in establishing a regular yoga practice.

Additionally, intervention participants who engage in the post-intervention focus groups will receive a meal during the focus group and a \$25 Tango Gift Card as a thank you for their feedback and time.

### **13.0 Withdrawal of Participants**

#### 13.1 Withdrawal Circumstances:

Because participants will be rigorously screened for participating, we will not withdraw any participants from the study. Only participants who are eligible and pass the screening will be recruited for the study. However, participants can assent or withdraw from the study at any given point, they will not be questioned nor will face penalty.

#### 13.2 Withdrawal Procedures:

This is a voluntary study, so participants can withdraw at any time during the study without any penalty or consequences. Once a participant withdraws from the study, there will be no attempt to collect additional data from them.

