### **3.0 Study Endpoints/Events/Outcomes**

#### **3.1 Primary Endpoint/Event/Outcome:**

This is a feasibility study, therefore the primary endpoints of interests are related to feasibility and acceptability of the intervention.

- Feasibility: Recruitment of participants - 200 women recruited and screened; 76 women (16 for Aim 1 focus groups and 60 for pilot intervention) enrolled and consented
- Feasibility: Retention and adherence -  $\geq 80\%$  of intervention participants attend  $\geq 80\%$  of intervention sessions
- Feasibility: Fidelity of intervention delivery -  $\geq 90\%$  of each videotaped session is delivered as planned based on training
- Feasibility: Intervention materials and resources - 100% of intervention materials and resources are delivered as planned
- Feasibility: Assessment measures -  $\geq 80\%$  intervention and control participants rate the assessments as not too burdensome;  $\geq 90\%$  intervention and control participants will complete baseline, post-intervention and 3-month follow-up assessments
- Acceptability: Intervention location, in-person classes, instructors, home-based resources -  $\geq 90\%$  intervention participants rate the various intervention components as acceptable
- Acceptability: Yoga intervention -  $\geq 90\%$  intervention participants rate intervention acceptable
- Safety: Adverse events - Zero severe adverse events (causes major disruption to participant's life, e.g., sprain, broken bone, CV event, death), zero moderate adverse events (causes minor inconvenience to participant, e.g., fainting spell, sore muscles for more than 3 days) and  $<10\%$  of participants report mild adverse events (no major impact, e.g., headache, sore muscles for 2-3 days)

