#### 13.3 Termination Procedures:

It is highly unlikely that any one would be terminated from the study by the research staff, but participants may choose to withdraw and terminate their participation. In those cases, all available data may potentially still be used in data analysis.

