## **14.0 Risks to Participants**

### 14.1 Foreseeable Risks:

Formative assessment and post-intervention focus groups: N/A

Pilot intervention: The potential risks to participants assigned to the yoga intervention, including psychological, social, and legal, are considered minimal. The potential adverse events anticipated in our intervention would be injuries due to participation in yoga (e.g., muscle strain, fainting, falling) as well as other complications from comorbidities such as obesity, hypertension, diabetes and medication use. Participants will be instructed to call their healthcare provider and notify the research staff if they experience an injury or any adverse event. As a proactive measure, a detailed plan for monitoring risks, tracking and reporting adverse events will be established at the start of the study. Adverse events will be classified as severe (cause major disruption to participant's life, e.g. sprain, broken bone, cardiovascular event, death), moderate (causes minor inconvenience to participant, e.g. fainting spell, sore muscles for >3 days), and mild (no major impact on participant, e.g. headache, sore muscles for 2-3 days). Any adverse events will be reported to the DSMB and IRB. If an adverse event does occur, the only alternative to participation in the intervention is not to participate, which eligible participants are able to opt out.

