## **17.0 Statistical Considerations**

### 17.1 Data Analysis Plan:

Aims 1-3. Feasibility, acceptability, and safety. Descriptive statistics of survey variables will be compared to the benchmarks in Table 6. For *recruitment*, we will record: a) the count of women

who express interest, b) weeks elapsed to screen 200 women, and c) number enrolled and consented as a % of the targets – 16 for focus groups and 60 for the pilot intervention. For *retention and adherence*, we will compute % of participants who attend  $\geq 80\%$  of the yoga sessions by tracking attendance to all in-person sessions. For *intervention fidelity*, [name] will analyze the videotaped yoga sessions using established criteria to enumerate the number of planned specific yoga components that were completed as a percentage of the total. For *feasibility* we will compute the percentage of participants who: a) receive the materials and resources throughout the intervention, b) rate the assessments as ‘not too burdensome’ on a multiple choice question, and c) complete baseline, post-intervention, and follow-up assessments. For *acceptability* we will compute the percentage of participants who rate the various intervention components as acceptable. For *safety* we will track all adverse events experienced by participants, report them to the UMN IRB, and compare to the benchmarks. If benchmark goals are not met, we will explore why they were not met during the post-intervention focus groups in hopes of gaining substantive information to address the missed benchmark goals in the future trial.

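### Data collection stops at withdrawal with no exception for adverse events, so an injury behind a withdrawal may go unrecorded or ungraded, which can only favour passing the safety benchmark

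*Combined protocol and SAP*

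**What the plan says.** Section 3.1 states that "the primary endpoints of interests are related to feasibility and acceptability of the intervention" and lists safety among them. The benchmark is zero severe events, zero moderate events, and fewer than 10% of participants with mild events. Muscle soreness lasting 2-3 days is an example of mild; beyond 3 days it is moderate.

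Section 17.1 (Aims 1-3) says "we will track all adverse events experienced by participants, report them to the UMN IRB, and compare to the benchmarks". It does not say how women who have left count in that comparison. The only missing-data rule stands in the Aim 4 paragraph.

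On leaving, 13.1 says "participants can assent or withdraw from the study at any given point, they will not be questioned nor will face penalty", and 13.2 says "Once a participant withdraws from the study, there will be no attempt to collect additional data from them". On data already held, 13.3 says "In those cases, all available data may potentially still be used in data analysis".

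Adverse events are picked up in two stated ways: a questionnaire given weekly during the study (10.2), and an instruction to tell the research staff about any injury or adverse event (10.2 and 14.1).

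**The concern.** A promise to capture every adverse event and a rule that ends all contact for data at withdrawal cannot both be kept for a woman who leaves because she was hurt. The missing information would be related to the outcome itself. That is the worst pattern for a benchmark set at zero, where one event decides the result.

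Two losses are possible. An injury between the last weekly questionnaire and withdrawal is not elicited, so it reaches the record only if she volunteers it. An event already reported but still open may be left at too low a grade, because soreness that looks mild on day 2 becomes moderate after day 3.

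At stake is whether a result of zero moderate or severe events can be read as evidence of safety when the next trial is planned.

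**Working it through.** The plan gives no expected event rate, withdrawal rate or precision for the safety benchmark, so there is no stated figure to reproduce. The check covers direction first, then a range of assumed sizes.

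**Inputs from the document**
- Arm size: 30 yoga, 30 control (4.1, 5.1).
- Benchmark: 0 severe, 0 moderate, <10% mild (3.1).
- Completion of assessments: at least 90% of intervention and control participants (3.1).

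**Inputs assumed, not in the document**
- p, the true risk per yoga woman of a moderate or severe event: 2%, 5%, 10%.
- m, the share of affected women whose event is never recorded: 0, 10%, 25%, 50%.

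**Direction.** An unrecorded event lowers the count. Dropping the injured woman from the denominator as well does not reverse this: with k recorded events and one missed, k/(n-1) < (k+1)/n whenever k+1 < n. Leaving a moderate event graded as mild also helps, because one moderate event fails the benchmark outright while one mild event need not.

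**Moderate and severe events.** Treating women as independent, the chance of recording none is

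P(zero recorded) = (1 - p(1 - m))^n, with n = 30.

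| p | m = 0 | m = 10% | m = 25% | m = 50% |
|---|---|---|---|---|
| 2% | 0.98^30 = 0.545 | 0.982^30 = 0.580 | 0.985^30 = 0.635 | 0.99^30 = 0.740 |
| 5% | 0.95^30 = 0.215 | 0.955^30 = 0.251 | 0.9625^30 = 0.318 | 0.975^30 = 0.468 |
| 10% | 0.90^30 = 0.042 | 0.91^30 = 0.059 | 0.925^30 = 0.096 | 0.95^30 = 0.215 |

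**One missed event.** With 0 of 30 recorded, the exact two-sided 95% upper limit is 1 - 0.025^(1/30) = 11.6%. If the truth is 1 of 30 (3.3%), the upper limit is 17.2%.

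**Mild events.** The benchmark in 3.1 refers to participants, while several neighbouring items specify intervention participants, so the denominator could be 30 or 60. Below 10% means at most 2 of 30 (2/30 = 6.7%; 3/30 = 10.0% fails) or at most 5 of 60 (5/60 = 8.3%; 6/60 = 10.0% fails). At an assumed true mild rate of 15%, the binomial chance of passing with m = 0, 25% and 50% is 0.151, 0.329 and 0.607 on 30 women, and 0.097, 0.319 and 0.706 on 60.

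**Room for leavers.** The 90% completion target is still met with 3 of 30 non-completers if applied by arm, or 6 of 60 overall. A few women could leave without any other benchmark necessarily drawing attention to it.

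**The case against.** The plan has safeguards, and they narrow the gap. Women are told to report injuries, the questionnaire is weekly, every session ends with a sharing circle (4.1) and a short survey (5.2), and 13.3 allows data gathered before withdrawal to be used. An injury is lost only if it surfaces at none of these contacts and the woman then leaves the whole study before her next questionnaire. That stands as a limit on size. It does not close the gap: apart from the weekly questionnaire these routes depend on her volunteering the injury or were built for another purpose, and none is stated to continue after withdrawal.

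The promise in 13.1 that she will not be questioned may mean only that she will not be challenged. That is a fair reading, but 13.2 ends data collection on either reading.

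Three stronger inferences are tempting and are not supported.

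- A reader might infer that the protocol itself steers injured women out of data collection, since 14.1 says "If an adverse event does occur, the only alternative to participation in the intervention is not to participate". That sentence concerns the intervention; 13.2 concerns withdrawal from the study. Stopping yoga is not stated to trigger 13.2, and the low-attendance focus groups in 4.1 suggest that women who attend little remain in the study.
- A reader might infer that nobody would follow an unresolved injury. Women are directed to their own healthcare provider, 20.2 provides for IRB and DSMB review, and 10.2, 14.1 and 20.1 refer to monitoring plans whose detail is not given here. What can be said is that this document states no follow-up after withdrawal.
- A reader might infer that any single missed event changes the result. It does so only if it is the sole moderate or severe event, or if the mild count sits just at its limit.

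**Conclusion.** The point holds in a limited form. Section 13.2 is an explicit rule without a safety exception. It conflicts with the undertaking in 17.1, and any event lost or under-graded through it moves a primary benchmark toward passing. The direction follows from the text and needs no assumption.

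The size cannot be determined, because no event or withdrawal rates are given. Under an assumed 5% risk, the effect on the chance of a clean moderate-and-severe record runs from slight (21% to 25% when a tenth of events are lost) to large (47% when half are). Nothing in the document supports a loss as high as half; that column is an upper illustration. The change is worth making because it is cheap and because a zero-event result cannot be interpreted without knowing how many women left with unknown status.

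**What to change.** **Sections 13.1 and 13.2.** State that stopping yoga is not withdrawal from the study, and that women who stop stay on the weekly adverse-event questionnaire and the scheduled assessment visits. For a woman who withdraws from the study itself, offer one voluntary closing contact using the existing adverse-event form, with an optional reason for leaving. If she agrees, record the outcome and final grade of any open event. Her right to leave without penalty is unchanged.

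**Section 17.1.** Report the safety benchmark on all randomised women, with the denominator stated. Beside it give the number who left and the number whose adverse-event status is unknown. A count that treats every unknown leaver as an event may be shown only as a labelled worst-case bound, because one such leaver would fail a zero-event limit whatever the cause.

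**Cost.** Protocol and consent wording, and one short call per leaver with a form already in use. Some women will decline, and the reported safety figure may look less favourable.

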#### 13.3 Termination Procedures:

It is highly unlikely that any one would be terminated from the study by the research staff, but participants may choose to withdraw and terminate their participation. In those cases, all available data may potentially still be used in data analysis.

## **14.0 Risks to Participants**

### 14.1 Foreseeable Risks:

Formative assessment and post-intervention focus groups: N/A

Pilot intervention: The potential risks to participants assigned to the yoga intervention, including psychological, social, and legal, are considered minimal. The potential adverse events anticipated in our intervention would be injuries due to participation in yoga (e.g., muscle strain, fainting, falling) as well as other complications from comorbidities such as obesity, hypertension, diabetes and medication use. Participants will be instructed to call their healthcare provider and notify the research staff if they experience an injury or any adverse event. As a proactive measure, a detailed plan for monitoring risks, tracking and reporting adverse events will be established at the start of the study. Adverse events will be classified as severe (cause major disruption to participant's life, e.g. sprain, broken bone, cardiovascular event, death), moderate (causes minor inconvenience to participant, e.g. fainting spell, sore muscles for >3 days), and mild (no major impact on participant, e.g. headache, sore muscles for 2-3 days). Any adverse events will be reported to the DSMB and IRB. If an adverse event does occur, the only alternative to participation in the intervention is not to participate, which eligible participants are able to opt out.

### 14.2 Reproduction Risks:

N/A

### 14.3 Risks to Others:

N/A

## **15.0 Incomplete Disclosure or Deception**

### 15.1 Incomplete Disclosure or Deception:

There is no incomplete disclosure or deception to be utilized in this study.

## **16.0 Potential Benefits to Participants**

### 16.1 Potential Benefits:

Formative assessment focus groups: No direct benefits are expected.

Pilot RCT: Participants enrolled in the yoga intervention will potentially receive the direct health benefits associated with regularly practicing yoga.

## **17.0 Statistical Considerations**

### 17.1 Data Analysis Plan:

Aims 1-3. Feasibility, acceptability, and safety. Descriptive statistics of survey variables will be compared to the benchmarks in Table 6. For *recruitment*, we will record: a) the count of women

who express interest, b) weeks elapsed to screen 200 women, and c) number enrolled and consented as a % of the targets – 16 for focus groups and 60 for the pilot intervention. For *retention and adherence*, we will compute % of participants who attend  $\geq 80\%$  of the yoga sessions by tracking attendance to all in-person sessions. For *intervention fidelity*, [name] will analyze the videotaped yoga sessions using established criteria to enumerate the number of planned specific yoga components that were completed as a percentage of the total. For *feasibility* we will compute the percentage of participants who: a) receive the materials and resources throughout the intervention, b) rate the assessments as ‘not too burdensome’ on a multiple choice question, and c) complete baseline, post-intervention, and follow-up assessments. For *acceptability* we will compute the percentage of participants who rate the various intervention components as acceptable. For *safety* we will track all adverse events experienced by participants, report them to the UMN IRB, and compare to the benchmarks. If benchmark goals are not met, we will explore why they were not met during the post-intervention focus groups in hopes of gaining substantive information to address the missed benchmark goals in the future trial.

**Aim 4. Targeted Outcomes.** Per the NCCIH’s “Pilot Studies: Common Uses and Misuse”, the research team do not intend to evaluate the efficacy of the intervention. The behavioral and biological outcome data will be used to inform the design of the future trial by identifying feasibility/adherence problems with measures and suggesting effect size expectations. Data will be cleaned for errors and outliers, checked for normality, and transformed if necessary. The primary behavioral outcome will be time spent sitting/lying down from the activPAL3 as the gold standard measure of sedentary time. The research team will also analyze standing, stepping, sit-stand transitions, and moderate and vigorous physical activity data from the activPAL. Blood pressure (systolic and diastolic average of three measurements), perceived stress, anthropometry and other exploratory measures will be analyzed similarly. If **missing data** exceed 10% multiple imputation will be performed in addition to complete case analysis. For this pilot, we will report 95% confidence intervals.

Proposed statistical analyses are outlined above.

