## 4.0 Study Intervention(s)/Interaction(s)

### 4.1 Description:

Formative assessment focus groups: After the research team revises the intervention strategies, the newly revised intervention strategies, including yoga sequence, will be presented and discussed during two focus groups of 6-8 sedentary African-American women. Please note that if the focus group participants propose intervention strategies different from what is expected by the MPIs, the MPIs will submit modifications to the IRB. Due to COVID-19 restrictions, these focus groups will take place virtually approximately in April - June 2021.

Yoga intervention: Please note that although we are anticipating conducting the yoga pilot intervention in-person, it is dependent on whether it is safe to have face-to-face contact due to COVID-19. If it is deemed unsafe to have face-to-face contact, the MPIs will submit a modification to IRB to reflect this change. Additionally, if it is safe to conduct the intervention face-to-face, the MPIs will submit the University-required "Sunrise Plan" outlining risk mitigation related to COVID-19.

Participants engaged in the formative assessment focus groups may be invited to be a part of the pilot RCT. 60 participants will be randomly assigned to the yoga intervention (n=30) or control condition (n=30). It is anticipated that the yoga intervention will be a hybrid delivery (combination of in-person and virtual) (June – August 2022) at two intervention locations, 612 Jungle and The Zen Bin. There will be no contact with control participants during the implementation of the yoga intervention. The yoga intervention components are:

- Hybrid, 60-minute yoga sessions will take place three times per week for 12 weeks to include a sharing circle at the end of each session. Participants will unite in a sharing circle to provide feedback as a group on how the practice felt and strategies for integration into ones' daily life. Specifically, each session will include gentle hatha yoga which includes physical poses combined with stretching, breathing and some meditation. A proposed session would include:
  - Warm-Up: Controlled Breathing Meditation & Mindfulness (10 minutes): Mindful breathing (4-6 second inhales/exhales) through nose to increase focus on yoga practice and to build internal heat to better prepare the body for movement
  - Warm-Up: Gentle Movement (5 minutes): Child's, Cat/cow, Thread the needle, Side puppy

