  - Active Movement: Strength, Flexibility & Balance Poses (20 mins):
  - Cool Down: Stretching Poses (10 mins): Cobbler's, Seated forward fold, Legs up the wall, Happy baby, Spinal twist
  - Cool Down: Resting Pose (5 mins): Final resting pose on back using props
  - Sharing Circle & Wrap-Up (10 mins): Group gathers in circle and share feedback about yoga session

These classes will be held in-person, but there will be a synchronous option for participants to join virtually. Yoga sessions will be led by certified yoga instructors from the greater Twin Cities metro area. As preparation for the pilot RCT, they will participate in intervention-specific training developed by research staff regarding (1) instructing yoga as part of a scientific study, and (2) the practice of restorative yoga for race-based trauma. They will be provided yoga sequences outlined by research staff and quality control data will be collected as described in section 15.2.

- A private Facebook group will be set up to keep participants connected to each other, thus further promoting collectivism, and for the research staff to maintain contact and share information with participants. Participants will be able to post freely to the Facebook page to stay connected, offer encouragement, and provide accountability to attend the weekly yoga sessions. Research assistants will keep track of the number of posts and "likes" each participant makes. Research staff will use Facebook to maintain contact and to share information with participants: 1) provide a weekly reminder for upcoming yoga sessions and workshops; 2) inform/remind participants of the biweekly themes of the sessions – there will be a new theme every other week (i.e., weeks 1, 3, 5, 7, 9, 11); and 3) remain accessible to participants for assistance or requested information participants may need. This contact will be virtual.

- To align with and reinforce the biweekly themes established for the weekly yoga sessions (i.e., common yoga poses, the importance of breath, strengthening your core), biweekly, hybrid workshops will be offered. These workshops will take place during weeks 2, 4, 6, 8, 10, and 12 and will be specialty classes that allow participants additional exposure to meditation and breathing and longer class formats so they can delve deeper into yogic philosophy and practice. These workshops will be held in-person, but there will be a synchronous option for participants to join virtually.

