Data collection: Yoga intervention and control participants (n=60) will complete baseline (March – May 2022), post-intervention (September – October 2022), and 3-month follow-up measures (January – February 2023) in-person at the University of Minnesota’s Epidemiology Clinical Research Center.

Post-intervention focus groups: Four groups (high attendance and low attendance from each intervention location) of randomly chosen intervention participants (anticipated n~20) will be invited to participate in a post-intervention focus group to assess intervention feasibility, acceptability, and safety with the overall program and specific components, and in order to inform program improvements. Focus groups will take place at the Epidemiology Clinical Research Center.

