### 5.2 Study Procedures:

Formative assessment focus groups will be conducted in April - June 2021. Data collected from these focus groups will be qualitative feedback on the proposed intervention strategies. The focus group guide is submitted with this IRB application.

Data collected directly related to the pilot RCT yoga intervention will be:

- Quality control data to make sure the yoga movements follow protocol and are safe for participants will be collected during the implementation of the yoga intervention. One yoga session will be randomly selected biweekly (during weeks 2, 4, 6, 8, 10, and 12) and videotaped so the content can be analyzed based on the established criteria related to poses, breathing and meditation. During these videotaped quality control sessions, participants will be asked to wear the activPAL to assess activity intensity.
- Acceptability of yoga classes will be assessed during the yoga intervention via a short self-reported survey after each yoga session. The survey is included with this application.
- Three, in-person data collection time points: baseline (March – May 2022), post-intervention (September – October 2022), and 3-month follow-up measures (January – February 2023). Data to be collected during these time points are:
  - Sedentary behavior will be assessed with the activPAL3 micro accelerometer (PAL Technologies, Glasgow, United Kingdom) for seven consecutive days at

- baseline before the start of the intervention, during three randomly selected weeks over the course of the 3-month intervention, and for one week at both the post-intervention and 3-month follow-up periods. The activPAL provides a valid and reliable measure of posture (sitting/lying vs. standing) for free-living settings and uses a transducer suitable for detecting lower intensity movements. The activPAL will be waterproofed using medical grade adhesive covering and attached to the midline of the thigh using a breathable, hypoallergenic tape. This method allows for the monitor to be worn continuously without removing for bathing or other water-based activities (a valuable feature that reduces missing data).

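### The primary adherence benchmark is computed from attendance at in-person sessions, although every class may be joined live online

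*Combined protocol and SAP*

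**What the plan says.** Section 3.1 lists "Feasibility: Retention and adherence" among the primary endpoints. The benchmark is that at least 80% of intervention participants attend at least 80% of the intervention sessions. Nothing there restricts how a session is attended.

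Section 4.1 anticipates that the "yoga intervention will be a hybrid delivery (combination of in-person and virtual"). The schedule is "Hybrid, 60-minute yoga sessions will take place three times per week for 12 weeks", and on mode it adds: "These classes will be held in-person, but there will be a synchronous option for participants to join virtually". The six biweekly workshops carry the same option. No cap on virtual joining is given for either.

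Section 17.1 (Aims 1-3) computes the percentage of participants who attend at least 80% "of the yoga sessions by tracking attendance to all in-person sessions". It does not mention virtual attendance.

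Two other places bear on attendance. Section 4.1 forms the post-intervention focus groups by "high attendance and low attendance from each intervention location", without naming the source of the attendance data. Section 5.2 assesses acceptability "via a short self-reported survey after each yoga session".

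**The concern.** The endpoint in 3.1 is about sessions of a hybrid programme, but the computation in 17.1 is tied to in-person sessions. If the computation is followed literally, a woman who uses a route the protocol offers her is scored as absent. The resulting figure would mix two things: adherence to the programme as designed, and preference for being physically present.

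Feasibility is the primary purpose of this study, and 17.1 intends missed benchmarks to inform the future trial. An adherence figure that is too low for this reason could lead the team to change a programme that women were in fact following.

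There is a possible second effect. If the same count sorts women into the high and low attendance focus groups, a woman who mostly joins online would be placed with the low attenders. Those groups are also where missed benchmarks are to be explored. Discussion there may reveal that women were joining online, but it cannot recover counts that were never logged.

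**Working it through.** The plan gives no sample-size or power figure for this benchmark, so there is nothing to reproduce. The check is threshold arithmetic on the plan's own numbers.

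**Inputs**

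- Classes: 3 per week for 12 weeks (4.1), so 3 x 12 = 36.
- Workshops: 6 (4.1).
- Individual threshold: 80% of sessions (3.1, 17.1).
- Group threshold: 80% of intervention participants (3.1).
- Intervention arm: 30, or 27 at the stated minimum (11.1).
- Virtual uptake: not given.

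**Individual threshold, classes only**

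- Needed: 0.80 x 36 = 28.8, so 29 classes.
- A woman who attends all 36 can have at most 36 - 29 = 7 uncounted classes (7/36 = 19%). She fails at 8 (28/36 = 78%).
- One virtual class every two weeks: (36 - 6)/36 = 30/36 = 83%, which meets the threshold.
- One virtual class every week: (36 - 12)/36 = 24/36 = 67%, which fails.
- A woman who attends 32 of 36 (89%) fails once 32 - 29 + 1 = 4 of them are virtual.

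**Individual threshold, workshops included**

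- Sessions: 36 + 6 = 42. Needed: 0.80 x 42 = 33.6, so 34.
- Full attendance fails at 42 - 34 + 1 = 9 virtual sessions.
- One virtual class a week, with all workshops attended in person: (42 - 12)/42 = 30/42 = 71%, which fails. Any virtual workshop lowers this further.

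The point therefore does not depend on whether workshops count.

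**Group threshold**

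- Arm of 30: 0.80 x 30 = 24 women needed; 7 short gives 23/30 = 77%, a miss.
- Arm of 27: 0.80 x 27 = 21.6, so 22 needed; 6 short gives 21/27 = 78%, a miss.

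Taken together: if all 30 women attended every class, but 7 of them each joined 8 or more classes online, the benchmark would be reported as missed at 77% when attendance by either mode was 100%.

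**Illustration under assumptions that are not in the documents**

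Suppose every woman attends all 36 classes, sessions and women are independent, and all women share one virtual proportion. In-person-only counting then gives:

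| Virtual share (assumed) | P(a woman has at least 29 counted) | P(at least 24 of 30 women) |
|---|---|---|
| 10% | 0.976 | about 1.00 |
| 20% | 0.566 | 0.007 |
| 30% | 0.112 | <0.001 |

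Counting both modes gives 1.00 throughout. A common share makes the drop sharper than it would be if uptake varied between women. The conclusion rests on the counts above, not on this table.

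**Is virtual attendance recorded elsewhere?**

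- The post-session survey in 5.2 is described as measuring acceptability, and its form is not in the text.
- The online tracking in 4.1 covers Facebook posts and likes.
- The high and low attendance split implies that some attendance record exists, but gives neither its source nor its mode.

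**The case against.** The best reply is that 17.1 may not exclude anyone. Section 4.1 describes the classes as held in person, with virtual joining as one way to attend them. On that view, in-person sessions are simply the scheduled live classes, as distinct from the home-based material. Section 3.1 supports this by listing "Intervention location, in-person classes, instructors, home-based resources" as separate components, and 19.1 describes a catalog of recorded classes. Section 12.5 even calls the whole programme face-to-face, so the documents use such terms loosely.

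This reading is possible, and no section states that virtual joins are excluded. But no section states that they are included either, and the inclusion criteria in 9.1 use in-person components to mean physical presence, in the context of vaccination or a negative test. Even on the softer reading, the plan does not say how a virtual join is recorded. Two analysts could follow 17.1 in good faith and report different results for a primary endpoint.

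Three further points stand in part:

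- Some sources cannot be checked. Section 17.1 refers to benchmarks in a Table 6 that is not in the available text, and class-roll details may sit in operational documents.
- The virtual-attendance patterns used above are illustrations, because uptake is unknown.
- The benchmark is descriptive, with no test or progression rule, so the harm is limited to a misread feasibility result.

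It is also fair to say that in-person attendance alone would be a legitimate, stricter target. In that case 3.1 should say so.

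**Conclusion.** The concern holds and should be fixed. On its plain wording, the rule in 17.1 omits a form of attendance that 4.1 permits and that 3.1 does not exclude. Any resulting error is downward. Eight virtual classes out of 36 (22%) are enough to reclassify a woman with perfect attendance, and seven such women out of 30 are enough to turn a met benchmark into a missed one.

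The conclusion assumes that 17.1 is applied as written and that no separate log of virtual joins exists outside the available text. How far the reported figure would actually be off cannot be estimated, because expected virtual uptake is not given. Confidence is medium because of the softer reading.

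**What to change.** In 17.1, replace the clause on tracking in-person attendance with wording such as:

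> by recording attendance at every scheduled yoga class, whether in person or by synchronous virtual joining, with the mode logged for each participant at each class. The benchmark counts both modes; in-person-only attendance is also reported.

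Use the same term for a session in 3.1 and 17.1, and state whether the six workshops are in the denominator; that choice is the team's. Apply the same attendance definition to the high and low attendance focus groups in 4.1. If the team wants in-person attendance alone as the target, 3.1 and 17.1 should both say so, and mode should still be logged.

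The cost is one sentence in 17.1, one matching term in 3.1, a cross-reference for the focus groups, and an in-person/virtual code on the class roll. The one drawback is that a log-in is weaker evidence of participation than physical presence. Reporting the in-person figure alongside makes that visible.
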